**7) Risks to Subjects**

The risks involved in this study are minor. Minimal risks in this study include bruising, more rarely inflammation or infection, and fainting during the blood draws. One might expect one such episode of bruising or fainting once per ten blood draws. An adverse event rate exceeding once per five blood draws will be reported to the IRB and the NIH.

 Mount Sinai	Protocol Name:	Multi-level supermarket discounts of fruits and vegetables on intake and health
	Principal Investigator:	[name]
	Primary Contact Name/Contact Info:	[name] [contact] [name] [contact]
	Date Revised:	8/7/20
	Study Number:	HS#: 16-00407 GCO#: 16-1050

All subjects will be made aware that their food purchasing in the supermarket will be tracked.

In light of the global pandemic, participants are at risk of contracting COVID-19 infections when visiting the clinical research unit facility. According to the CDC website, there is an additional risk of severe COVID-19 infections for individuals who:

- Are 65 years and older
- Live in a nursing home or long-term care facility
- Have underlying medical conditions, particularly if not well controlled, including:
  - Chronic lung disease or moderate to severe asthma
  - Serious heart conditions
  - The immunocompromised (cancer treatment, smoking, bone marrow transplant or whole organ transplantation, immune deficiencies, poorly controlled HIV/AIDS and prolonged use of corticosteroids and other immune-weakening medications)
- People with severe obesity ( $BMI \geq 40.0 \text{ kg/m}^2$ )
- People with diabetes
- People with chronic kidney disease undergoing dialysis
- People with liver disease

In line with these guidelines, we have created a COVID-19 High Risk Screening Tool to track each potential participant's risk for severe illness from COVID-19 infection. Those with 2 or more risk factors will not be recruited for participation at this time.

## 8) Provisions for Research Related Harm/Injury

We do not anticipate participants needing any medical or psychological resources as a result of an adverse event associated with this study. But, participants will receive a referral for treatment at the end of the study (if indicated) as well as any requested health information.

## 9) Potential Benefits to Subjects

Increasing F&V intake in this overweight group is likely to lead to relatively greater health benefits and possible weight reduction than in those of normal weight, who are more likely to be

 Mount Sinai	Protocol Name:	Multi-level supermarket discounts of fruits and vegetables on intake and health
	Principal Investigator:	[name]
	Primary Contact Name/Contact Info:	[name] [contact] [name] [contact]
	Date Revised:	8/7/20
	Study Number:	HS#: 16-00407 GCO#: 16-1050

consuming adequate F&V. All subjects will also receive a brief nutritional counseling session at end with recommendations and education regarding the benefit of increasing F&V intake in their daily diet. Participants will receive discounts on fruits, vegetables and non-caloric sodas.

A direct benefit would be the nutritional session at end of the study and referral for treatment (if appropriate) as well as the health information provided to the subjects. Participants will be monetarily compensated for their participation. Those subjects may lose weight. Participants may benefit from increased awareness of health factors related to foods that might improve their ability to control their weight in the future. Thus, it is possible that the proposed study will enhance the well-being of the subjects. The potential benefit to the field of obesity intervention and prevention outweighs the risks posed to subjects in this study.

## 10) Provisions to Protect the Privacy Interests of Subjects

All experimental procedures will be explained and questions answered. The risks and benefits of participation will be described before obtaining a signed IRB-approved informed consent form. No pressure will be exerted on the subjects to participate. Minor concerns raised by subjects (e.g., embarrassment about reporting body weight) will be addressed by research staff. Efforts will be made to ensure that visits to the Clinical Research Unit (CRU) at the Endocrinology Division or at Quest Diagnostics are as comfortable as possible for participants. Research staff members will be HIPAA-sensitive when communicating with participants in person, over the phone, and over email, ensuring that protected health information (PHI) is only communicated with the participant themselves or other parties whom the subject has granted consent to share information with. Research staff will approach all shoppers at grocery stores to participate, as all shoppers would benefit from increased fruit and vegetable consumption. Subjects will also have the opportunity to express interest to research staff.

## 11) Economic Impact on Subjects

4

## 12) Payments to Subjects

Subjects will be compensated by check: \$50 for the screening visit, \$85 for each of the following five study visits, with a \$100 bonus for study completion, for a possible total of \$575. The check will also include compensation for mass transit travel (projected value: \$5.50) to and from the hospital. Subjects whose travel by public transportation might exceed 30 min will be given check reimbursement for taxis. These moderate incentives remunerate subjects for time and travel for assessment visits (and not for the initial supermarket visit), and are the same across groups. Thus, the remuneration is unlikely to influence the study outcome and should not reduce the

	Protocol Name:	Multi-level supermarket discounts of fruits and vegetables on intake and health
	Principal Investigator:	[name]
	Primary Contact Name/Contact Info:	[name] [contact] [name] [contact]
	Date Revised:	8/7/20
	Study Number:	HS#: 16-00407 GCO#: 16-1050

generalizability of the findings to everyday shopping behavior, food intake, body weight, and metabolic risk factors.

### 13) Consent Process

- If you will be following “SOP HRP-090 Informed Consent Process for Research”, after addressing the points above, indicate this. Otherwise, also describe:
  - The role of the individuals listed in the application as being involved in the consent process.
  - The time that will be devoted to the consent discussion.
  - Steps that will be taken to minimize the possibility of coercion or undue influence.
  - Steps that will be taken to ensure the subjects’ understanding.
  - Describe any tools that will be utilized during the consent process

#### ***Waiver or Alteration of the Consent Process***

If the Human Research involves a request for a waiver or alteration of the consent process, review the “CHECKLIST HRP-415 Criteria for Waiver or Alteration of the Consent Process” and make sure your submission provides adequate information for the IRB to assess the criteria for approval. It is highly recommended that you provide additional information here to address each of the criteria for approval (e.g. impracticability).

Informed consent will be obtained by the study team after the study is explained and all questions answered. Approximately 25 minutes will be devoted to the consent discussion. The informed consent form will have first been approved by the IRB at the Icahn School of Medicine at Mount Sinai. No vulnerable populations will be included in this study.

The risks and benefits of participation will be described before obtaining a signed IRB-approved informed-consent form. No pressure will be exerted on the subjects to participate.

### 14) Process to Document Consent in Writing

*This section always applies. Describe whether and how consent of the subject will be documented in writing. If using the standard PPHS consent template, simply indicate this.*

*If you are requesting a waiver of documentation of consent (consent will be obtained but the subject or representative will not sign a consent document) review the “CHECKLIST HRP-416*

Protocol Name:	Multi-level supermarket discounts of fruits and vegetables on intake and health
Principal Investigator:	[name]
Primary Contact Name/Contact Info:	[name] [contact] [name] [contact]
Date Revised:	8/7/20
Study Number:	HS#: 16-00407 GCO#: 16-1050

*Criteria for Waiver of Written Documentation of Consent" and address each of the criteria for approval. Describe whether you will be using a consent document without a signature page, some other kind of script, etc.*

*Note: If HIPAA applies, the HIPAA regulations regarding documentation are stricter and may require that a signature be obtained. In most cases, the use of the combined consent/HIPAA authorization is most appropriate and so the waiver request may not be granted for consent if it will be required for HIPAA.*

The standard IRB consent template will be used to document subject consent in writing either in-person or virtually on REDCap using a secure Zoom interface.

## 15) Vulnerable Populations

*Indicate specifically whether you will include (target) or exclude each of the following populations:*

Include	Exclude	Vulnerable Population Type
		Adults unable to consent
		Individuals who are not yet adults (e.g. infants, children, teenagers)
		Wards of the State (e.g. foster children)
		Pregnant women
		Prisoners

N/A

## 16) Multi-Site Human Research (Coordinating Center)

N/A

## 17) Community-Based Participatory Research

N/A

## 18) Sharing of Results with Subjects

One of the ways we will disseminate study results will be through the Columbia Community

 
Mount Sinai
	Protocol Name:	Multi-level supermarket discounts of fruits and vegetables on intake and health
	Principal Investigator:	[name]
	Primary Contact Name/Contact Info:	[name] [contact] [name] [contact]
	Date Revised:	8/7/20
	Study Number:	HS#: 16-00407 GCO#: 16-1050

Partnership for Health (CCPH) site. Allegiance affiliated supermarket' owners and staff as well as merchants from the Greater Harlem community and subjects will be invited to hear presentations of the findings. The site is funded by the Community Engagement Core Resource (CECR) at the Irving Institute for Clinical and Translational Research.

If during the Screening Visit or any of the subsequent Study Visits one of the subjects' questionnaire responses, biochemical data points, or physical assessments indicates an increased risk for disease from baseline (or previously absent disease with higher risk at baseline), then the subject will be encouraged to speak with their primary care physician. The research team will make these data available to the PCP.

**19) External IRB Review History**

N/A

**20) Control of Drugs, Biologics, or Devices**

N/A

Multi-level Supermarket Discounts of Fruits and Vegetables' Impact on Intake and Health
PI: [name]
NCT04178824
Document Date: 8-1-2023

Statistical Analysis Plan

Linear mixed effects modeling was performed to evaluate the group-by-time interaction of all outcomes from the intent-to-treat (ITT) sample, as a primary analysis, and the per-protocol sample, as a secondary analysis. The ITT sample was comprised of participants with at least one post-randomization measurement. The per-protocol sample was comprised of all participants who completed the study. Primary outcome measures were grams (g) of fruit, vegetable, non-caloric beverage intake, and body weight (expressed in kilograms (kg)). Secondary dietary outcomes were high-ED food intake (g), total fat intake (g), and daily energy intake (kcal). Secondary clinical outcomes were BMI (kg/m²), percent body fat, waist circumference (cm), metabolic risk factors (fasting glucose (mg/dL), cholesterol (mg/dL), and blood pressure (mmHg). The linear mixed model included the group-by-time interaction term, where time was the within-subjects factor and group was the between-subjects factor (fixed effects), and the participant as the random effect to obtain the within-person differences in response to the intervention. No covariates were added to the main model because there were no baseline differences in covariates between discount groups and the RCT study design reduces between-group differences (29). First, an omnibus test was performed to test the overall effect of the group-by-time on interaction on the outcome variables. Then, a planned comparison approach using difference-in-difference contrast (DiD) was done to evaluate the differential change in primary outcome variables. The main comparison of interest was the change between groups between the baseline and the first 16 weeks of the intervention (the mid-point of the intervention period), 32 weeks of the intervention (the end of the intervention period), and 16 weeks post-intervention (the end of the follow-up period). A sensitivity analysis was also performed on the ITT sample by adding key covariates to the model: sex, age at enrollment, season at enrollment, primary supermarket, COVID presence, and income level. The presence of COVID was assigned if the COVID-19 pandemic and lockdown period occurred during the intervention between 2/20/20 and 4/6/2021. The absence of COVID-19 was assigned if the COVID-19 pandemic period happened prior to or after the intervention. Income level was a dichotomous variable: above or below the median income in NYC. Estimated means and 95% confidence intervals are shown in tables and figures. Missing data was assumed to be missing at random (MAR). Two-tailed $P < .05$ was considered statistically significant. RStudio (RStudio version 2023.12.0 Build 369) was used to analyze all data.

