### 4) Resources Available to Conduct the Human Research

Enrollees will be 360 men and women ranging from 18 to 65 y.o., and estimating a dropout rate of 37.5%, this should lead to 225 completers. We are excluding those under 18 y.o. for two reasons: 1) There are relatively few customers under the age of 18 who are the primary shoppers for the household; and 2) we wish to recruit participants who are no longer growing in stature. The upper limit of 70 y.o. was used because older participants may experience non-volitional weight loss that is sometimes associated with aging. To reduce potential COVID exposure for high risk populations, we are reducing the age limit to 65. Similarly, the upper limit of BMI  $50 \text{ kg/m}^2$  was initially chosen because the degree of obesity  $>50 \text{ kg/m}^2$  is often associated with morbidity. However, to reduce risk to high-risk populations, the upper limit is reduced to  $40 \text{ kg/m}^2$ . We are limiting our sample to primary shoppers of the household who do  $\geq 30\%$  of total grocery shopping at their selected Allegiance affiliated supermarket, and regularly use their loyalty cards, to ensure that each participant generates sufficient purchasing data for analysis and that the intake data collected reflects the discount intervention's effects on purchasing. The exclusion criteria are designed to eliminate potential confounding factors that may affect purchasing or consumption behavior or body weight.

Participants will be carefully monitored using resources at Mt. Sinai Morningside/St. Luke's Clinical Research Unit (CRU). The unit director, [name] has agreed to provide both the space and resources necessary to conduct all of the minimally invasive medical procedures written into the protocol, [name], MD will also serve as the safety officer for this trial. [name] has experience conducting clinical research studies and a good understanding of obesity research. She will review the reports sent by the research coordinator, [name], MS, and will use the checklist attached to this document to determine whether there is any corrective action, trigger of an ad hoc review or stopping rule that should be communicated to the PI, the hospital IRB, and the NIH. In

	Protocol Name:	Multi-level supermarket discounts of fruits and vegetables on intake and health
	Principal Investigator:	[name]

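### The SAP's primary ITT set is a modified ITT: it drops randomised participants who have only baseline data, which can bias the difference-in-difference contrasts under MAR if early loss relates to baseline differently by arm.

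*SAP*

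**What the plan says.** The SAP makes its ITT sample the primary analysis and defines it by follow-up: "The ITT sample was comprised of participants with at least one post-randomization measurement". The secondary set is completers.

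On the model it says "The linear mixed model included the group-by-time interaction term, where time was the within-subjects factor and group was the between-subjects factor (fixed effects"), with "the participant as the random effect to obtain the within-person differences in response to the intervention". The primary outcomes are then examined by contrasts from baseline: "a planned comparison approach using difference-in-difference contrast (DiD) was done to evaluate the differential change in primary outcome variables". The main model is unadjusted: "No covariates were added to the main model because there were no baseline differences in covariates between discount groups". On missing data: "Missing data was assumed to be missing at random (MAR").

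The one sensitivity analysis keeps the same people: "A sensitivity analysis was also performed on the ITT sample by adding key covariates to the model".

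The protocol (section 4, and again in 5c) plans for substantial loss from 360 enrolled: "estimating a dropout rate of 37.5%, this should lead to 225 completers". Participants learn their discount level at Study Visit 2 (week 8), and the next clinic visit is at week 24 (section 5f).

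**The concern.** Membership of the primary set depends on something that happens after randomisation, namely supplying a follow-up measurement. The label ITT therefore does not describe the set. That much needs no assumption.

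The statistical question is whether it matters. MAR lets dropout depend on observed data, including arm and the baseline outcome. A likelihood-based mixed model handles such dropout if the observed data enter it, including the baselines of those who leave early. Here baseline is one of the modelled time points and the main model has no covariates, so those baselines are the only route by which the model could correct for baseline-related early loss. The SAP removes them. If the people who remain have a higher or lower mean baseline in one arm than in another, their later values regress towards the mean by different amounts, and the contrast counts that as an intervention effect.

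No planned analysis would reveal this. The completer set is narrower, and the covariate-adjusted run uses the same sample. The outcomes most exposed are the recalled-intake ones, which include the measure used to power the study (protocol, Specific Aims).

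**Working it through.** **The plan's own figure.** 360 × (1 − 0.375) = 225, as sections 4 and 5c state. This is total loss from enrolment. It includes withdrawals for low spending or unreachability during the 8-week baseline (section 5f), so it only caps the share of randomised participants with baseline data alone. Neither document gives that share.

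**Formula.** Let the outcome have SD 1 at each time and within-person correlation ρ, the same in both arms. Let m be the mean baseline shift, in SD, of those kept in an arm, relative to all randomised in that arm.

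- Mean change among those kept = true change + (ρ − 1) × m.
- Bias of the discount-minus-control contrast = (ρ − 1) × (m_D − m_C) = (1 − ρ) × (m_C − m_D).
- With everyone randomised in the model, the fitted change becomes (change among those kept) + (ρ − 1) × (baseline mean of all − baseline mean of those kept). The last bracket is −m, so the error cancels and the bias is zero.

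**When the bias is zero.** If early loss is unrelated to baseline, or depends on arm only, then m_C = m_D = 0. If it depends on baseline identically in both arms, then m_C = m_D. If ρ = 1, the first factor vanishes.

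**Assumed scenarios (none of these inputs is in the documents).** Early loss follows a logistic model in the standardised baseline outcome. A negative slope means that low-baseline people leave. The shifts m come from numerical integration over a normal baseline.

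| Early loss, control / discount | Slope per SD, control / discount | m_C | m_D | ρ = 0.3 | ρ = 0.45 | ρ = 0.6 | ρ = 0.95 |
|---|---|---|---|---|---|---|---|
| 27% / 12% | −1 / 0 | 0.229 | 0 | 0.16 | 0.13 | 0.09 | 0.01 |
| 27% / 12% | −1 / −1 | 0.229 | 0.108 | 0.085 | 0.067 | 0.049 | 0.006 |
| 20% / 12% | −0.5 / 0 | 0.096 | 0 | 0.067 | 0.053 | 0.038 | 0.005 |
| 27% / 12% | −0.5 / −0.5 | 0.129 | 0.058 | 0.049 | 0.039 | 0.028 | 0.004 |
| 15% / 10% | −0.5 / −0.5 | 0.073 | 0.049 | 0.017 | 0.013 | 0.010 | 0.001 |
| 27% / 12% | +1 / 0 | −0.229 | 0 | −0.16 | −0.13 | −0.09 | −0.01 |

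First row, ρ = 0.3: (1 − 0.3) × (0.229 − 0) = 0.160. Reversing the control slope reverses the sign.

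**Simulation check.** For the first row (true effect 0, 120 per arm, a further 12% random loss per later interval, 1,500 trials per correlation), the week-40 bias under the SAP's set was 0.155, 0.125 and 0.091 SD. The empirical standard errors were 0.173, 0.159 and 0.134, so the bias was 0.90, 0.79 and 0.68 of a standard error. With all randomised kept, the bias was −0.004, 0.000 and −0.001. A separate simulation of this scenario gave two-sided false-positive rates of about 15%, 13% and 10% under the SAP's set, against about 5% with all randomised.

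**Fitted-model check.** With ρ = 0.5, 20% early loss per arm and slopes of −0.7 and +0.7, m_C = 0.130 and m_D = −0.130, so the predicted bias is 0.5 × 0.260 = 0.130. Over 60 simulated trials of 120 per arm, the SAP set differed from the all-randomised fit by 0.131 (Monte Carlo standard error 0.004).

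**Extreme bound.** Opposite slopes give larger values: 0.182 at ρ = 0.3 with 20% per arm, and 0.332 if the whole 37.5% in each arm had baseline data only. The second treats all planned loss as early loss after randomisation. It marks a ceiling for that slope, not an expectation.

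**The case against.** The strongest objection is that nothing in the documents shows early loss related to baseline differently by arm. A reader might infer that the SAP's set biases the primary analysis whenever MAR holds. It does not: several MAR patterns, including purely random loss at unequal rates, give no bias at all. A reader might also take the likely motive, controls learning at week 8 that their discount starts only at week 57, as proof of bias in favour of the discount. That motive is an effect of arm. Alone it gives zero bias, and no document says that low rather than high baseline eaters would leave. The protocol (Innovation) offers the delayed discount as a way to limit disappointment, and section 12 pays all arms alike with a completion bonus. All of this stands.

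The excluded group may also be smaller than the week-24 visit suggests. Dietary recalls are made by phone around the middle of each period (section 5f, Measures). Someone who gives a recall after week 8 and leaves before week 24 has a post-randomisation measurement and stays in, at least for intake. Body weight would barely be affected if its correlation is near 0.95. Both points stand and narrow the concern.

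Finally, the SAP is written in the past tense, so changing the primary set now is post hoc. That calls for disclosure but does not defeat the change: all randomised participants is what the ITT label already promises, and the present set can be reported beside it.

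**Conclusion.** The set called ITT is a modified ITT, and it discards baseline data that the SAP's own model and MAR assumption would use. This follows from the text. That the exclusion can bias the contrasts is also established. That it did so is not.

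Bias requires early loss that shifts the retained baseline mean differently between arms, together with a within-person correlation below 1. In the tabulated scenarios its absolute size is about 0.01 to 0.16 SD at correlations of 0.3 to 0.6, in either direction, and about 0.01 SD or less at 0.95. Opposite dependence in the two arms would exceed that range. The loss rates, slopes and correlations are all assumed, and the formula takes equal variances and the same correlation in each arm. The point is worth acting on because the exclusion brings no benefit and keeping these participants removes this source of bias.

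**What to change.** Replace the SAP's definition with: *The ITT sample is all randomised participants, analysed in the arm assigned; those with only pre-randomisation data remain in the mixed model.*

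Then:

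- keep the present set as a sensitivity analysis, labelled modified ITT;
- state that the change was made after the original analysis;
- report by arm the number randomised, the number with no post-randomisation measurement, and the mean baseline outcome of those excluded and those kept.

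The cost is one sentence and a re-run on data already held. If early loss was harmless, the two analyses should agree closely and the report can show it.
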